### Version Control Record

Version	Creation / Revision
1.0	September 30 th , 2019
2.0	November 8 th , 2019
3.0	November 29 th , 2019
4.0	September 14 th , 2020

## 1 SYNOPSIS

Name of Sponsor/Company: PharmaEssentia Japan	
Name of Investigational Product: P1101 (ropeginterferon alfa-2b)	
Name of Active Ingredient: Ropeginterferon (P1101) is a mono-pegylated form of the P1040 drug intermediate (Proline-IFN $\alpha$ -2b) that has been reacted with a 40 kDa branched PEG-aldehyde. The pegylation site is predominantly at the N-terminal proline of the P1040 drug intermediate; more precisely, the drug substance P1101 is an N-terminally mono-pegylated drug intermediate of P1040.	
Title of Study: Phase 2 single arm study of efficacy and safety of P1101 for polycythemia vera (PV) patients for whom the current standard of treatment is difficult to apply.	
Study Countries and Center(s): Japan	
Coordinating Investigator: [name] [name] (Yamanashi University)	
Planned Studied Period: September 2019 to August 2021	Phase of development: Phase 2
Objective: The primary objective is to demonstrate safety and efficacy of P1101 in terms of complete hematologic response (CHR) without phlebotomy with Japanese patients diagnosed with PV for whom the current standard of treatment is difficult to apply.  The primary endpoint “complete phlebotomy-free hematologic response (CHR)” is defined as a condition that meets the following hematological criteria, hematocrit (<45%), WBC ( $\leq 10 \times 10^9/L$ ), platelets ( $\leq 400 \times 10^9/L$ ) and require no phlebotomy at month 9 and month 12.  The secondary objective is to demonstrate safety and efficacy of P1101 in terms of changes in Hct, WBC, PLT, spleen size, molecular and cytogenetic response from baseline, time to requiring no phlebotomy, numbers of phlebotomy required, time to response, duration of response maintenance, ratio of CHR rates of subjects with/without prior treatment with HU and Proportion of subjects without thrombotic events.	
Study Design: This is a Phase 2 single arm study to investigate efficacy and safety of P1101 for adult Japanese patients with PV. Eligible patients will be treated with P1101, starting at 100 $\mu$ g (or 50 $\mu$ g in patients under another cytoreductive therapy). The dose should be gradually increased by 50 $\mu$ g every two weeks (in parallel, other cytoreductive therapy should be decreased gradually, as appropriate) until stabilization of the hematological parameters is achieved (hematocrit <45%, platelets <400 $\times 10^9/L$ and leukocytes <10 $\times 10^9/L$ ). The maximum recommended single dose is 500 $\mu$ g injected every two weeks.  At week 36 (month 9) and week 52 (month 12), the primary study endpoint, phlebotomy-free CHR, will be analyzed. After completion of the 52-week study duration, provision and administration of P1101, collection of the long-term follow up information (blood parameters, molecular and	

cytogenetic data, safety parameters and as also the optional bone marrow data) will be continued until the drug becomes commercially available for all study subjects..

**Number of Patients (planned):**

30 patients (all recruited in Japan)

**Diagnosis and Main Criteria for Inclusion and Exclusion:**

**• Inclusion Criteria**

1. Male or female patients  $\geq 20$  years old at the time of informed consent
2. Patients diagnosed with PV according to the WHO 2008 or WHO 2016 criteria
3. PV patients for whom the current standard of treatment is difficult to apply. Patients with a documented history of refractory to HU are excluded (see Appendix 6; modified ELN criteria based on "Barosi et al, 2010 ELN criteria", (Barosi et al. 2010)).
  - Younger patients (long-term treatment is anticipated)
  - Patients who are categorized as low risk, but cytoreduction is recommended due to disease-related signs and symptoms (headache, dizziness, pruritus, night sweats, fatigue, erythromelalgia, vision disorders, scintillating scotoma, early satiety, abdominal distension).
  - Patients with HU intolerance (see Appendix 6; modified ELN criteria based on "Barosi et al, 2010 ELN criteria", (Barosi et al. 2010))
4. Total HU treatment duration shorter than 3 years (cumulatively) at screening
5. For cytoreduction naïve patients only: PV in need of cytoreductive treatment, defined by fulfilling as one or more of the following criteria at baseline:
  - at least one previous well documented major cardiovascular PV-related event in the medical history
  - poor tolerance of phlebotomy (defined as a phlebotomy/ procedure-related adverse event causing significant adverse impact on the patient and limiting ability to apply phlebotomy with the intention to keep Hct  $<45\%$ )
  - frequent need of phlebotomy (more than one phlebotomy within last month prior entering the study)
  - platelet counts greater than  $1000 \times 10^9/L$  (for two measurements within the month prior treatment start)
  - leukocytosis (WBC  $>10 \times 10^9/L$  for two measurements within the month prior treatment start)
  - manifestation of disease-related signs and symptoms (headache, dizziness, pruritus, night sweats, fatigue, erythromelalgia, vision disorders, scintillating scotoma, early satiety, abdominal distension)
6. Adequate hepatic function defined as total bilirubin  $\leq 1.5 \times$  upper limit normal (ULN), international normalized ratio (INR)  $\leq 1.5 \times$  ULN, albumin  $>3.5 \text{ g/dL}$ , alanine aminotransferase (ALT)  $\leq 2.0 \times$  ULN, aspartate aminotransferase (AST)  $\leq 2.0 \times$  ULN at screening
7. Hemoglobin (HGB)  $\geq 10 \text{ g/dL}$  at screening
8. Neutrophil count  $\geq 1.5 \times 10^9/L$  at screening
9. Serum creatinine  $\leq 1.5 \times$  ULN at screening
10. Hospital Anxiety and Depression Scale (HADS) score 0-7 on both subscales (Appendix 8).  
(Patients with a borderline of HADS score (score 7 but  $<10$ ) or patients with necessity (expected

benefits are higher than the risks) based on investigators' discretion are required to receive following assessment by psychiatric specialist to confirm the eligibility for IFN $\alpha$  therapy.).

11. Males and females of childbearing potential, as well as all women  $<2$  years after the onset of menopause, must agree to use an acceptable form of birth control until 28 days following the last dose of the study drug
12. Written informed consent obtained from the patient or the patient's legal representative, and ability for the patient to comply with the requirements of the study

• **Exclusion Criteria**

1. Patients with symptomatic splenomegaly
2. Previous use of IFN $\alpha$  for any indication
3. Any contraindications or hypersensitivity to interferon-alfa
4. Co-morbidity with severe or serious conditions which may impact patient participation in the study in investigator's opinion
5. History of major organ transplantation
6. Pregnant or lactating females (Breastfeeding women are not allowed to enter this study by discontinuing breastfeeding)
7. Patients with any other medical conditions, which in the opinion of the Investigator would compromise the results of the study or may impair compliance with the requirements of the protocol, including but not limited to:
  - 7.1. History or presence of thyroid dysfunction (clinical symptoms of hyper- or hypothyroidism) of the autoimmune origin, except late stages cases on the oral thyroid substitution therapy, where potential exacerbation under interferon therapy will not constitute any further harm to the patient
  - 7.2. Documented autoimmune disease (e.g., hepatitis, idiopathic thrombocytopenic purpura [ITP], scleroderma, psoriasis, or any autoimmune arthritis)
  - 7.3. Clinically relevant pulmonary infiltrates and pneumonitis at screening, patients with a history of interstitial pulmonary disease
  - 7.4. Active infections with systemic manifestations (e.g., bacterial, fungal, hepatitis B [HBV], hepatitis C [HCV], or human immunodeficiency virus [HIV]) at screening
  - 7.5. Evidence of severe retinopathy (e.g., cytomegalovirus retinitis [CMV], macular degeneration) or clinically relevant ophthalmological disorder (due to diabetes mellitus or hypertension) based on the ophthalmological assessment by specialists.
  - 7.6. Uncontrolled depression
  - 7.7. Previous suicide attempts or at any risk of suicide at screening
8. Uncontrolled diabetes mellitus (HbA1c level of  $> 7\%$  at baseline)
9. History of any malignancy within for the past 5 years (except Stage 0 chronic lymphocytic leukemia [CLL], basal cell, squamous cell, and superficial melanoma believed to be cured)
10. History of alcohol or drug abuse within the last year
11. History or evidence of post polycythemia vera-myelofibrosis (PPV-MF), essential thrombocythemia, or any non-PV MPN;
12. Presence of circulating blasts in the peripheral blood within the last 3 months
13. Use of any investigational drug(s), or investigational drug combinations  $<4$  weeks prior to the first dose of study drug or not recovered from effects of prior administration of any investigational agent

With regard to acetylsalicylic acid, which will be considered as the background treatment in the

study unless contraindicated, the following contraindications are known for low-dose acetylsalicylic acid: history of hypersensitivity to Bayaspirin or any salicylic acid preparation, peptic ulceration, bleeding tendency, aspirin-induced asthma (asthma attack induced by NSAID etc.) and its history, pregnant women within 12 weeks of estimated date of confinement, baby with a low birth weight/newborn infant/ suckling infant. If any of the contraindications are observed, the patient may still participate in the study without being administered acetylsalicylic acid.

### **Investigational Product and Reference Therapy, Dosage, and Mode of Administration:**

Patients who meet the inclusion criteria and who do not meet the exclusion criteria will start therapy with P1101 (ropginterferon alfa-2b). The investigational product will be administered subcutaneously every 2 weeks at the starting dose of 100 µg every two weeks (or 50 micrograms in patients under another cytoreductive therapy). The dose should be gradually increased by 50 µg every two weeks (in parallel, other cytoreductive therapy should be decreased gradually, as appropriate) until stabilization of the hematological parameters is achieved (hematocrit <45%, platelets <400 x 10^9/L and leukocytes <10 x 10^9/L). The maximum recommended single dose is 500 µg injected every two weeks. The dose will be maintained at the highest level which can be tolerated and delivers best possible disease response.

Low-dose aspirin (acetylsalicylic acid) (75-150 mg/day per local practice) will be given during the 12 months of study treatment, unless contraindicated.

Phlebotomy is performed aiming at a hematocrit < 45%. When the hematocrit value is 45% or higher, phlebotomy is performed. The volume of phlebotomy per procedure should be 200 to 400 mL per one phlebotomy while monitoring the circulatory dynamics such as blood pressure and pulse. In the elderly and patients with cardiovascular disorders, a small volume (100 to 200 mL) should be considered to avoid rapid changes in hemodynamics.

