## 6.2 Secondary Objectives:

The secondary objective is:

- to demonstrate safety and efficacy of P1101 in terms of changes in Hct, WBC, PLT, spleen size, molecular and cytogenetic response from baseline, time to requiring no phlebotomy, numbers of phlebotomy required, time to response, duration of response maintenance, ratio of CHR rates of subjects with/without prior treatment with HU and Proportion of subjects without thrombotic events.
- to assess the pharmacokinetics (PK) of P1101 and population PK (PPK) analysis
- to assess the relationship between exposure and key efficacy and safety endpoint using exposure-response (E-R) analysis
- to assess the immunogenicity of P1101

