## **14 PRIOR AND CONCOMITANT THERAPY**

All medications (i.e., over-the-counter drugs and blood products) taken within 3 months (12 weeks) prior to the administration of the study drug, as well as, all concurrent therapies will be recorded in the relevant eCRF pages. All prior nondrug therapies, as well as, all surgeries will be recorded in the relevant eCRF pages. Dose, route, unit frequency of administration, indication for administration, and dates of medication will be captured. Any concomitant medications or changes thereof must be recorded at each visit. If the change influences the subjects' eligibility to continue in the trial, the Sponsor must be informed.

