### **15.3.1.2 Other Efficacy Measurements**

There will be disease response assessments at Weeks 0, 12, 24, 36, and 52 of treatment with P1101. During these times, changes in Hct, WBC, PLT, spleen size, molecular response from baseline, time to requiring no phlebotomy, numbers of phlebotomy required, time to response, duration of response maintenance, ratio of CHR rates of subjects with/without prior treatment with HU and Proportion of subjects without thrombotic events will be assessed.

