3.6 Study Periods

Screening period lasts from signature of informed consent to the Week 0 (Visit 1).

Treatment period lasts from Visit 1 to the "End of Treatment" visit or premature discontinuation.

End-of-Treatment (EOT) is the last visit in treatment period.

Post-Treatment Safety follow-up is visit lasting from "End of Treatment" visit (V27) or time of study discontinuation. It is also the End of Study Visit.

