4.3.4.2 Secondary Variables

- Changes in HCT, WBC, PLT and Spleen Size from baseline
 - Absolute values and changes will be computed over study timepoint (Months 3, 6, 9 and 12)
- Time to first phlebotomy
 - Time to first phlebotomy is defined as the time interval from first dosing to first time when subject experiences a phlebotomy procedure. Subjects who completed the study and never had a phlebotomy procedure will be censored at the end of the study (Month 12). Subjects who discontinued from the study prior to any phlebotomy procedure will be censored at the time of discontinuation.
- Numbers of phlebotomy
 - Number of phlebotomy procedures experienced will be categorized as 0, 1, 2, 3 and >3.
- Disease response over time (DRT)
 - DRT will be derived from hematology parameters (Hematocrit <45% without phlebotomy (at least 3 months since last phlebotomy), and platelets $\leq 400 \times 10^9/L$, and WBCs $\leq 10 \times 10^9/L$). Central laboratory assessments will be used for disease response assessment at Weeks 12, 24, 36, 52. Patients, who withdraw early for any reason, will be classified as treatment failures in visits that they did not complete. Disease response based on local laboratory assessment will be analyzed as a sensitivity analysis if the data is available.

Protocol P1101 in Japanese PV (A19-201)

- Time to first peripheral blood count response

Time to first peripheral blood count response is defined as the time interval from first dosing to first time when achieving disease response (Hematocrit <45% without phlebotomy (at least 3 months since last phlebotomy), and platelets $\leq 400 \times 10^9/L$, and WBCs $\leq 10 \times 10^9/L$). Subjects who completed the study and never achieved response will be censored at the end of the treatment (Month 12). Subjects who discontinued prior to achieving a disease response will be censored at the time of discontinuation.

- Duration of peripheral blood count response maintenance:

Duration of response maintenance will be calculated as number of days starting from assessment visit when the response was achieved till date (excluding) of assessment visit when the response was lost. If more response period occurred within one patient, the longest period will be used for analysis. Number of days will be divided by 30.5 and results presented in months. Only subjects with response will have the duration.

- Change from baseline of *JAK2* allelic burden over time

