4.3.5.4 Number of phlebotomies

Number of phlebotomies during treatment phase will be summarized using descriptive statistics and frequency/percentage for categories of 0,1,2,3 and >3.

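### The phlebotomy count is one treatment-phase total per patient, with no split by period and no allowance for follow-up time, so it cannot show a change in phlebotomy need

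*Protocol*

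**What the plan says.** Protocol 6.2, repeated in the Synopsis and SAP 2.2.2, sets a secondary objective of demonstrating efficacy on a list of measures that includes "time to requiring no phlebotomy, numbers of phlebotomy required, time to response, duration of response maintenance". Protocol 15.3.1.2 then states "There will be disease response assessments at Weeks 0, 12, 24, 36, and 52 of treatment with P1101" and names the number of phlebotomies among the items assessed at those times. Protocol 5.5 says a lower phlebotomy frequency is expected.

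The SAP's treatment of the measure is short:
- 4.3.4.2: "Number of phlebotomy procedures experienced will be categorized as 0, 1, 2, 3 and >3".
- 4.3.5.4: "Number of phlebotomies during treatment phase will be summarized using descriptive statistics and frequency/percentage for categories of 0,1,2,3 and >3".
- 3.6, which fixes the counting window: "Treatment period lasts from Visit 1 to the 'End of Treatment' visit or premature discontinuation".

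No count by period, no rate and no pre-treatment value is defined.

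On the procedure itself, the Synopsis and Protocol 14.1 say "The volume of phlebotomy per procedure should be 200 to 400 mL per one phlebotomy". For the elderly and patients with cardiovascular disorders, "a small volume (100 to 200 mL) should be considered to avoid rapid changes in hemodynamics".

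On prior treatment, Protocol 14 says "All prior nondrug therapies, as well as, all surgeries will be recorded in the relevant eCRF pages". It does not name phlebotomy there and sets no look-back for nondrug therapies.

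**The concern.** With no control arm, a change in phlebotomy need can be seen only against time on treatment or against a value from before treatment. The planned count has neither. The protocol sets out a time structure for this measure, and the SAP does not carry it forward.

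The counting window also closes when a patient discontinues. A patient followed for a short time has fewer procedures counted for that reason alone, and the summary cannot tell this apart from lower need.

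At stake is whether a measure named in the secondary objective can be interpreted. The primary analysis is not affected.

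**Working it through.** **Plan's own figure.** The documents give no numerical target for phlebotomies. Their only power figure concerns complete hematologic response and has no bearing here, so there is nothing to reproduce.

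**Step 1: timing.** Inputs are the 50 µg steps every two weeks from 100 µg or 50 µg up to 500 µg (Synopsis), the 3-month phlebotomy-free condition (Protocol 7.1), and the SAP's month of 30.5 days (4.3.4.2).

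On schedule, 500 µg is reached at (500 − 100)/50 × 2 = Week 16, or (500 − 50)/50 × 2 = Week 18. Take two illustrative completers:
- Patient A has phlebotomies at Weeks 2, 6, 10 and 14, then none. All fall within titration, and A can still be a responder at Months 9 and 12.
- Patient B has four in Weeks 40-52. B cannot be a responder at Month 12.

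A 12-week period is 84/30.5 = 2.75 months; the last, of 16 weeks, is 112/30.5 = 3.67 months.

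| | Planned total | Planned category | Count by period (0-12, 12-24, 24-36, 36-52) | Rate per month by period |
|---|---|---|---|---|
| A | 4 | >3 | 3, 1, 0, 0 | 1.09, 0.36, 0, 0 |
| B | 4 | >3 | 0, 0, 0, 4 | 0, 0, 0, 1.09 |

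The mean, median and range are computed from the same total, so they cannot separate A from B either.

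**Step 2: follow-up time.** One procedure in a patient who leaves at Week 12, against one in a completer: (1/12)/(1/52) = 4.3. Both are recorded as 1.

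The effect on the group mean depends on dropout, which the documents do not project. As an illustration, Protocol 5.3 reports 217 completers among 254 randomised in the earlier phase 3 study, so f = 37/254 = 14.6% did not complete. If the rate of procedures is constant and all leavers go at week t, the mean count is lowered by f × (1 − t/52):
- t = 12: 0.146 × 0.769 = 11.2%.
- t = 26: 0.146 × 0.5 = 7.3%.

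If procedures cluster early in treatment, the loss is smaller.

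**Step 3: do other planned outputs fill the gap?**
- Response at Weeks 12, 24, 36 and 52 (SAP 4.3.5.2) needs at least 3 months since the last phlebotomy, and so does the hematocrit-target count (4.3.5.3). Both carry timing, but only as yes/no combined with blood counts.
- Protocol 7.2 lists a time until phlebotomy is no longer needed. SAP 4.3.4.2 analyses time to the first phlebotomy. That is censored at discontinuation, so follow-up is handled there, but it dates the first procedure and not the end of the need.
- Listings (4.3.1.2) are chronological, but they are not a summary.

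None of these gives the number of phlebotomies over time.

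**Step 4: volume.** Within each band the range is twofold: 400/200 = 2 and 200/100 = 2. Across bands it is 400/100 = 4, so 800 mL could be 800/400 = 2 procedures or 800/100 = 8. The fourfold figure sets the top of the general band against the bottom of the band for the elderly and patients with cardiovascular disorders. It is a spread between patients.

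**The case against.** The strongest reply is that the objective asks for the number of phlebotomies required and the SAP reports it. A reader might infer that the secondary objective is itself about a reduction. The documents do not support that: the expected fall in frequency is stated only in Protocol 5.5, under risks and benefits. This limits the criticism to what the count can show.

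A reader might also infer that the plan is blind to timing. That is too strong. The primary endpoint and the by-visit response would separate patients A and B, and the descriptive statistics keep a count of 4 distinct from 8 even though both fall in >3. The limitation belongs to this one variable.

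The list in Protocol 15.3.1.2 also includes whole-study quantities such as duration of response, so the weeks may be collection times only. This stands in part: the text does not prescribe tabulation by period, but it supplies natural cut-points.

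A third tempting reading is that unequal volumes invalidate the count. They do not. The trial's own criterion is whether a phlebotomy took place, not how much was removed.

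Finally, the variable is missing from the endpoint list in Protocol 7.2, and Protocol 17.4.2 calls the secondary endpoints supportive. No success criterion depends on it. That is correct and limits the weight of the point.

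**Conclusion.** The point holds as a limitation of one supportive, descriptive variable. Followed as written, the SAP yields a total that cannot show whether phlebotomy need changed during treatment and that is lower for patients who leave early. For a single patient the rate behind the same count can differ 4.3-fold (Week 12 against Week 52). For the group mean the shortfall is about 7% to 11%, assuming dropout as in the earlier phase 3 study, departure at Week 26 or Week 12, and a constant rate.

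A reader might go further and infer that a pre-treatment count would let the trial demonstrate a reduction. The documents do not support that. Entry criterion 5 can admit cytoreduction-naive patients because of frequent recent phlebotomy, which inflates their prior count. In patients treated with hydroxyurea (HU) the prior count reflects that drug. It is also not established that the count is collected. The on-treatment split is the part of the remedy that rests on firm ground.

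**What to change.** In SAP 4.3.5.4, with a matching definition in 4.3.4.2:

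1. Keep the treatment-phase total and its categories.
2. Add, for Weeks 0-12, 12-24, 24-36 and 36-52, the number of patients under observation, the number of procedures, the patient-months of follow-up, and the rate per patient-month. Assign procedures by date, and end follow-up at the End of Treatment visit or premature discontinuation. The rate is needed because of early leavers and because the last period is 16 weeks.
3. If prior phlebotomies are captured on the eCRF, show the pre-treatment count over a stated look-back as descriptive context only, with the two cautions given above.
4. If volume is recorded, an optional supportive listing is enough.

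The periods should be read as a time trend, not as titration against maintenance: scheduled escalation runs to Week 16 or 18, and Protocol 12.1 allows up to 32 weeks to reach 500 µg.

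The cost is SAP wording and one extra table, settled before database lock. Phlebotomy dates are already needed for the 3-month phlebotomy-free criterion, so item 2 needs no new data. No change to phlebotomy practice is implied.
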